### 7.2 *Secondary endpoints*

Progression-free survival, overall survival, and duration of response will be calculated with 95% confidence intervals. Toxicity rates will also be calculated by category with 95% confidence intervals. With 20 subjects, we have a 88% chance of observing, at least once, any toxicity occurring at a rate of 10% or higher.

We will use response as the primary efficacy marker to investigate the relationship between changes in autophagy and protein lysine acetylation markers and the efficacy of treatment. We will summarize time-to-event outcomes (time to progression, survival time and duration of response) with Kaplan-Meier survival curves. We will also analyze toxicity including changes in counts, and degree of non-hematologic toxicity, according to the pharmacodynamic markers. Analyses of mutational profiles and correlatives from tumor biopsies (if obtained) will be exploratory.

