***1.3 Secondary Endpoints***

- 1.3.1 To describe the toxicity profile of the three drug combination
- 1.3.2 To measure overall survival, progression-free survival, and duration of response
- 1.3.3 To describe mutational profiles of responders and non-responders using next-generation sequencing
- 1.3.4 To evaluate the pharmacodynamics of entinostat by measuring protein lysine acetylation in peripheral blood mononuclear cells (PBMCs), and lymphocyte subsets

1.3.5 To assess and quantitate autophagy pharmacodynamics using Western blotting of PBMC extracts and serum markers

1.3.6 To describe gene expression alterations as result of therapy using paired biopsy specimens at baseline and 3 weeks (Phase II portion only, when funding available)

1.3.7 To analyze FOXO1 expression and subcellular localization as a marker of treatment effect using paired biopsy specimens at baseline and 3 weeks (Phase II portion only, when funding available)

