### ***2.5 Regorafenib Clinical Experience***

Regorafenib is a multikinase inhibitor with effects on angiogenesis via the VEGF pathway as well as various cell growth pathways. It is closely related to sorafenib, differing in structure by a single fluorine molecule. The principle tyrosine kinase targets of regorafenib include VEGFR1-3, PDGR- $\beta$ , KIT, RAF-1, B-RAF, B-RAFV600E, RET, and to a lesser extent FGFR2 and TIE2.

Phase I trials established a dosing regimen of 160 mg daily for 21 days of a 28 day cycle and demonstrated hand-foot syndrome, fatigue, diarrhea, and hypertension as the predominant side effects. Regorafenib demonstrated consistent bioavailability between subjects.  $T_{1/2}$  ranged from 20-40 hours, with relative stability of plasma concentrations between doses. It is metabolized into two pharmacologically active compounds, M2 and M5, which reach similar concentrations as the parent compound at steady state.

Regorafenib is an FDA-approved therapy for metastatic colorectal cancer that has progressed on prior therapy with 5-fluorouracil, oxaliplatin, irinotecan, anti-angiogenic therapy, and, if KRAS wild-type, anti-EGFR therapy. This approval was based on a proven survival benefit from the phase III CORRECT trial, which compared regorafenib to placebo in a 2:1 ratio in colorectal cancer that had progressed on all standard therapies. Participants randomized to regorafenib in that trial received 160 mg daily for three weeks out of a four-week cycle. Overall survival improved in the regorafenib arm to 6.4 months, compared to 5.0 months in the placebo arm (hazard ratio 0.77, 95% CI 0.64-0.94,  $p=0.0052$ ). Grade 3-4 toxicities in this trial with regorafenib included hand-foot syndrome (17%), fatigue (10%), diarrhea (7%), hypertension (7%), and rash (6%). Very few objective responses were seen with regorafenib (1% versus 0.4% with placebo), implying a cytostatic effect on the tumor.

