#### ***4.6 Duration of Treatment***

Patients will continue therapy on 28-day cycles until disease progression or the constraints of this therapy are deemed to be detrimental to the patient's health. In this event, the protocol should be discontinued. Furthermore, the protocol will be discontinued should the patient withdraw consent. All patients in whom protocol therapy has been discontinued will be followed for progression of disease and survival.

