#### ***4.7 Measurement of Response***

Patients will be assessed on regularly prescribed intervals in order to determine if there is evidence of disease progression. A CT or MRI of the abdomen/pelvis and chest (if thoracic disease is present) will be obtained at 8 and 16 weeks, then every 8-12 weeks per standard practice.

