#### 10.4.3 Duration of Response

Duration of overall response: The duration of overall response is measured from the time measurement criteria are met for CR or PR (whichever is first recorded) until the first date that recurrent or progressive disease is objectively documented (taking as reference for progressive disease the smallest measurements recorded since the treatment started). The duration of overall CR is measured from the time measurement criteria are first met for CR until the first date that progressive disease is objectively documented.

Duration of stable disease: Stable disease is measured from the start of the treatment until the criteria for progression are met, taking as reference the smallest measurements recorded since the treatment started, including the baseline measurements.

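### Duration of response has no death event, and 7.2 applies Kaplan-Meier to time to progression where PFS is the endpoint: deaths without documented progression are censored in the first and could be in the second

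*Combined protocol and SAP*

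**What the plan says.** The synopsis and section 1.3 name PFS as a secondary endpoint: "To measure overall survival, progression-free survival, and duration of response". The first sentence of section 7.2 repeats it: "Progression-free survival, overall survival, and duration of response will be calculated with 95% confidence intervals". That sentence gives no estimator, time origin, event list or censoring rule.

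The second paragraph of 7.2 is the only place that names a time-to-event method: "We will summarize time-to-event outcomes (time to progression, survival time and duration of response) with Kaplan-Meier survival curves". Time to progression stands where PFS would be expected. Neither term is defined anywhere in the document.

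Duration of response does have a written definition. The number 10.4.3 is used twice; the relevant section is the second, headed Duration of Response. It runs overall response "until the first date that recurrent or progressive disease is objectively documented", and complete response (CR) "until the first date that progressive disease is objectively documented". Death ends neither.

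Section 4.6 says that patients who stop protocol therapy "will be followed for progression of disease and survival". Section 4.7 says that imaging "will be obtained at 8 and 16 weeks, then every 8-12 weeks per standard practice".

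**The concern.** PFS and time to progression differ in one respect: whether a death without documented progression counts as an event. If it does not, a Kaplan-Meier analysis treats the patient as censored at death, as though progression could still have been observed later. Patients who die before a scan shows progression are unlikely to have the same outlook as those still under observation, so that censoring is informative. It also acts in one direction, in favour of the regimen.

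Such deaths are foreseeable. Section 2.5 reports of single-agent regorafenib: "Overall survival improved in the regorafenib arm to 6.4 months". Scans are eight or more weeks apart, and the note to Table 12 foresees patients who stop for deterioration before progression has been shown objectively. The trial has one arm, so its PFS and duration of response will be read against outside results. An estimate that leaves out deaths is not comparable with a PFS that counts them. A death caused by the three-drug combination itself would likewise not count against it.

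**Working it through.** **Plan's own figures.** The documents state no sample size, power or expected median for PFS, time to progression or duration of response. The one figure in 7.2 is the 88% chance of seeing a 10% toxicity at least once in 20 patients: 1 - 0.9^20 = 0.878. It reproduces and has no bearing here.

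**Step 1: direction.** At each event time the Kaplan-Meier estimate is multiplied by 1 - d/n, where d is the number of events and n the number at risk. Recoding a death from event to censored lowers d at that time and leaves n at every time unchanged. Every factor therefore stays the same or moves closer to 1, and the curve can never fall. This holds without any model.

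**Step 2: duration of response.** Section 7.1.2 gives a target response rate of 15%, at least 20 evaluable patients and 26 patients at the recommended phase II dose. Expected responders are 20 × 0.15 = 3.0 to 26 × 0.15 = 3.9. With so few, one death matters. Take an invented example of four responders with durations of 2 (death), 3, 5 and 8 months:
- Death as an event: the curve is 0.75 at 2 months and 0.50 at 3 months. Median 3 months.
- Death censored: the curve is 2/3 at 3 months and 1/3 at 5 months. Median 5 months.

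**Step 3: PFS against time to progression.** Let h be the constant hazard of the first event, progression or death, and f the share of first events that are deaths without documented progression. The PFS median is ln 2 / h. With deaths censored, the hazard is (1-f)h and the median is ln 2 / ((1-f)h). The ratio is 1/(1-f). For 6-month estimates, assume a true PFS median of 4 months: PFS at 6 months is 0.5^(6/4) = 0.354, and with deaths censored it is 0.354^(1-f).

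| Assumed f | Median ratio 1/(1-f) | 6-month estimate, deaths as events | 6-month estimate, deaths censored |
|---|---|---|---|
| 0% | 1.00 | 0.35 | 0.35 |
| 5% | 1.05 | 0.35 | 0.37 |
| 10% | 1.11 | 0.35 | 0.39 |
| 20% | 1.25 | 0.35 | 0.44 |
| 30% | 1.43 | 0.35 | 0.48 |

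A simulation with 26 patients, the same assumed median and follow-up of 6 to 18 months gave the same 6-month values to two decimals for f of 5% to 30%.

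**Step 4: is a non-zero f plausible?** The documents do not give f. As a rough indication only, an exponential curve with the cited median survival of 6.4 months puts deaths before the week-8 scan (8 × 7 / 30.4 = 1.84 months) at 1 - 0.5^(1.84/6.4) = 0.18. This is probably too high for patients selected under section 3.1, who must have ECOG status 0 or 1 and a life expectancy above 3 months. Some early deaths would also follow a scan that already showed progression.

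**The case against.** The strongest reply concerns PFS. The two lists in 7.2 run in parallel: PFS, overall survival and duration of response in the first; time to progression, survival time and duration of response in the second. Survival time is plainly a loose name for overall survival, so time to progression may well be a loose name for PFS. The synopsis, section 1.3 and the first sentence of 7.2 all say PFS. This stands. A reader might infer that the plan commits the analyst to censoring deaths in the PFS analysis, but no censoring rule is written and the documents do not support that. They support only that deaths could be censored if the Kaplan-Meier sentence is followed literally.

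The reply does not reach duration of response. There the end events are written out and death is not among them. An analyst could count deaths only by departing from the definition.

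Second, the size is not in the documents. Median survival does not tell us how many deaths precede documented progression. Eligibility limits very early deaths, section 4.6 continues follow-up after treatment stops, and the note to Table 12 asks for progression to be documented even then. This also stands: the percentages are illustrations, and the effect is nil if f is zero.

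Third, the consequences are limited. The only hypothesis test is on response rate (7.1.2), and section 2.8 bases further development on response rate. With three or four responders, a median duration will be imprecise under any definition. That argues for modest weight. It does not argue for leaving a one-directional error in a definition that is easily corrected.

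**Conclusion.** The point holds in two parts of different strength.

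- **Duration of response.** As written, overall response and CR both end only at documented recurrence or progression. A Kaplan-Meier analysis on that definition censors responders who die first, and the estimate can only be unchanged or too long.
- **PFS.** Section 7.2 uses two endpoint names and defines neither. If time to progression is meant literally, deaths without documented progression could be censored and the curve biased upward. If it is only a label, the defect is an inconsistent name and a missing definition.

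Under constant hazards the median would be overstated by a factor of 1.05 to 1.43 for an assumed f of 5% to 30%. Neither the range nor the hazard shape comes from the documents, so these figures should not be read as the expected bias. Nor should a reader infer that the main result is compromised: the response-rate test, its power and the sample size are untouched. This should be corrected before analysis, as a matter of secondary endpoints only.

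**What to change.** - **Section 7.2.** Replace time to progression with progression-free survival, defined as time from start of treatment to the first of RECIST progression or death from any cause. Patients with neither are censored at their last disease assessment.
- **Duration of Response (the second 10.4.3).** End both duration of overall response and duration of CR at recurrence or progression, or at death, whichever comes first. Renumbering one of the two sections would remove doubt about which is meant.
- **If time to progression is also wanted**, report it separately under its own name and treat death as a competing event.

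The cost is small. These are wording changes, and section 4.6 already provides for following patients for progression and survival after they stop therapy, so no new data item is needed. Reported medians may be somewhat shorter. Settling the wording now also removes the option of choosing the more favourable endpoint once the data are known.

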### 7.3 *Sample Size/Accrual Rate*

Phase I: The phase I study will involve six possible dose levels, although accrual at more than 3 or 4 levels is very unlikely. The total sample size will range from a minimum of 12 to a maximum of 24 patients. We expect accrual to be completed within 6-9 months.

Phase II: During the Phase II portion we will enroll up to 20 additional patients and expect an accrual time of approximately 1 year.

### 7.4 *Statistical Software*

All analyses, except as otherwise noted, will be performed using either SAS or STATA.

## 8.0 SAFETY AND ADVERSE EVENTS

### 8.1 Definitions

#### 8.1.1 Adverse Event

An adverse event (AE) is any symptom, sign, illness or experience that develops or worsens in severity during the course of the study. The CTC version 4.0 will be used to grade toxicity. Intercurrent illnesses or injuries should be regarded as adverse events. Abnormal results of diagnostic procedures are considered to be adverse events if the abnormality:

- Results in study withdrawal
- Is associated with a serious adverse event
- Is associated with clinical signs or symptoms
- Leads to additional treatment or to further diagnostic tests
- Is considered by the investigator to be of clinical significance

#### 8.1.2. Serious Adverse Event

Adverse events are classified as serious or non-serious. A serious adverse event is any AE that is:

- Fatal
- Life-threatening
- Requires or prolongs hospital stay
- Results in persistent or significant disability or incapacity
- A congenital anomaly or birth defect
- An important medical event
- Pregnancy

#### 8.1.3 Important Medical Events

Important medical events are those that may not be immediately life threatening, but are clearly of major clinical significance. They may jeopardize the patient, and may require intervention to prevent one of the other serious outcomes noted above. All adverse events that do not meet any of the criteria for serious should be regarded as non-serious adverse events.

## **8.2. *Post-study***

All unresolved adverse events should be followed by the investigator until the events are resolved, the patient is lost to follow-up, or the adverse event is otherwise explained. At the last scheduled visit, the investigator should instruct each patient to report any subsequent event(s) that the patient, or the patient's personal physician, believes might reasonably be related to participation in this study.

## **8.3 *Abnormal Laboratory Values***

A clinical laboratory abnormality should be documented as an adverse event if the abnormality is of a degree, typically at least grade 2 and not present as grade 1 or higher at baseline, that requires active management; e.g. change of dose, discontinuation of the drug, more frequent follow-up assessments, further diagnostic investigation.

## **8.4 *Hospitalization, Prolonged Hospitalization or Surgery***

Any adverse event that results in hospitalization or prolonged hospitalization should be documented and reported as a serious adverse event unless specifically instructed otherwise in this protocol. Any condition responsible for surgery should be documented as an adverse event if the condition meets the criteria for an adverse event.

Neither the condition, hospitalization, prolonged hospitalization, nor surgery are reported as an adverse event in the following circumstances:

- Hospitalization or prolonged hospitalization for diagnostic or elective surgical procedures for a preexisting condition. Surgery should not be reported as an outcome of an adverse event if the purpose of the surgery was elective or diagnostic and the outcome was uneventful.
- Hospitalization or prolonged hospitalization required to allow efficacy measurement for the study.
- Hospitalization or prolonged hospitalization for therapy of the target disease of the study, unless it is a worsening or increase in frequency of hospital admissions as judged by the clinical investigator.

### ***8.5 Recording of Adverse Events***

At each contact with the patient, the investigator must seek information on adverse events by specific questioning and, as appropriate, by examination. Information on all adverse events should be recorded immediately in the source document, and also in the appropriate adverse event module of the case report form (CRF). All clearly related signs, symptoms, and abnormal diagnostic procedures results should be recorded in the source document, though should be grouped under one diagnosis. All adverse events occurring during the study period must be recorded. The clinical course of each event should be followed until resolution, stabilization, or until it has been determined that the study treatment or participation is not the cause. Serious adverse events that are still ongoing at the end of the study period must be followed up to determine the final outcome. Any serious adverse event that occurs after the study period and is considered to be possibly related to the study treatment or study participation should be recorded and reported immediately.

### ***8.6 Reporting of Serious Adverse Events***

#### **8.6.1 Study Sponsor Notification by Investigator**

A serious adverse event must be reported to the study sponsor within 24 hours of the event. Report serious adverse events by phone and facsimile to:

[name]  
[contact]  
[contact]  
or via the HUP page operator at [contact]

At the time of the initial report, the following information should be provided:

- Study identifier
- Study Center
- Patient number
- A description of the event
- Date of onset
- Current status
- Whether study treatment was discontinued
- The reason why the event is classified as serious
- Investigator assessment of the association between the event and study treatment

### 8.6.2 IRB Notification by Investigator-sponsor

Reports of all serious adverse events (including follow-up information) must be submitted to the IRB within 10 working days, according to IRB guidelines.

#### Reporting Process to IRB

Principal Investigators are required to submit reports of unanticipated problems posing risks to subjects or others that are probably or definitely study related via the HS-ERA system within 10 working days of the event.

For reportable deaths, the initial submission to the IRB may be made by contacting the appropriate IRB coordinator as soon as the death is known, with a report via HS-ERA within 10 days if death is from underlying disease and within 24 hours if study related activity is considered contributory to the death.

### 8.6.3 FDA Notification by Investigator-sponsor, Voluntary

The study sponsor shall notify the FDA by telephone or by facsimile transmission of any unexpected fatal or life-threatening experience associated with the use of the drug as soon as possible but no later than 7 calendar days from the sponsor's original receipt of the information. If a previous adverse event that was not initially deemed reportable is later found to fit the criteria for reporting, the study sponsor will submit the adverse event in a written report to the FDA as soon as possible, but no later than 15 calendar days from the time the determination is made.

### 8.6.4 Sponsor Notification

The investigator must inform Syndax in writing using a SAE form or MEDWATCH 3500A form of any SAE within 24 hours of being aware of the event. The date of awareness should be noted on the report. The written report must be completed and supplied to Syndax within 24 hours/1 business day at the latest on the following working day. The initial report must be as complete as possible, including details of the current illness and (serious) adverse event, and an assessment of the causal relationship between the event and the investigational product(s). Information not available at the time of the initial report (e.g., an end date for the adverse event or laboratory values received after the report) must be documented on a follow-up report. A final report to document

resolution of the SAE is required. If this is a multicenter trial, participating study sites must report SAEs to Syndax as described and within 24 hours of awareness.

Participating sites should also report SAEs to the primary study site.

## **9.0. DATA HANDLING AND RECORD KEEPING**

### ***9.1 Confidentiality***

Information about study subjects will be kept confidential and managed according to the requirements of the Health Insurance Portability and Accountability Act of 1996 (HIPAA).

Those regulations require a signed subject authorization informing the subject of the following:

- What protected health information (PHI) will be collected from subjects in this study
- Who will have access to that information and why
- Who will use or disclose that information
- The rights of a research subject to revoke their authorization for use of their PHI

In the event that a subject revokes authorization to collect or use PHI, the investigator, by regulation, retains the ability to use all information collected prior to the revocation of subject authorization. For subjects that have revoked authorization to collect or use PHI, attempts should be made to obtain permission to collect at least vital status (i.e. that the subject is alive) at the end of their scheduled study period

